C-arm CBCT is a technology that allows for CT images of the vasculature, bone, and soft tissues to be generated utilizing the flat detectors of modern angiography machines. This is accomplished with high speed rotation of the C-arm around a supinely positioned patient while collecting an array of 2-dimensional x-ray projections. Separately SMART-RECON algorithms are used to reconstruct the projections in anatomic planes comparable to CT images. With recent advances in technology the post-processing of images can provide both anatomic and physiologic (perfusion) information using an intravenous injection of contrast dye. This high-quality C-arm CBCT angiography utilizes 1/3 of the radiation dose currently used in our clinical practice under conventional CT imaging technology. This technique has been validated by our previously published work¹⁷⁻¹⁹.

Study Objective

The objective of this proposal is to conduct a feasibility study of acetazolamide activated C-arm CBCTP to determine its application in the prediction of symptomatic cerebral vasospasm in patients with aneurysmal subarachnoid hemorrhage. Our initial plan is to obtain C-arm CBCTP pre- and post-intravenous infusion of 1 gram acetazolamide within 24 hours of symptom onset in aneurysmal subarachnoid hemorrhage patients. Our hypothesis is that some of these patients that will later develop clinical vasospasm of a degree sufficient to cause cerebral ischemia. We believe this cohort of patients will demonstrate altered cerebrovascular reactivity during the acetazolamide challenge at a time before there is either angiographic evidence of vasospasm or clinical evidence of abnormal perfusion. Thus far in the pilot study we have enrolled a total of 10 patients and are now planning to expand enrollment to 30 patients. The data we have collected from the research scans have thus far been reproducible and collected with clinical ease. There have been no complications with imaging acquisition and there have been no safety concerns for patients. Having so far achieved our objectives with the initial 10 patients we now hope to amend the protocol to allow for the larger cohort of 30 subjects. With this larger sample size we will not only continue to assess safety and reproducibility, but also will hope to capture a large number of patients who develop vasospasm in order further assess

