the utility of the research study in its application as a screening diagnostic tool to predict the subsequent occurrence of delayed vasospasm in subjects with an acute aneurysmal subarachnoid hemorrhage.

Study Methods

Inclusion criteria:

A total of 30 subjects will be enrolled in this pilot feasibility study. The following patients will be targeted for enrollment:

1. Patients with aneurysmal subarachnoid hemorrhage presenting to our institution within 24 hours of symptom onset.
2. Adults, 18 years of age or older
3. Women of childbearing potential must not be pregnant (urine pregnancy test will be required as is already done as part of standard of care)

Exclusion criteria:

Whether subjects will be invited to participate in this research will be based on the patient's medical condition and will be at the discretion of the treating physician. The following patients will be excluded automatically:

1. Contraindication to acetazolamide (i.e. sulfonamide allergy, renal or liver failure)
2. Contraindication to contrast media (Allergy or abnormal serum Cr and/or GFR based on current UW guidelines for IV contrast see Appendix A)
3. Renal insufficiency, history of renal failure or renal transplant
4. Hunt and Hess grade 1 and 5 (See Appendix B, as Grade 1 have lower yield for vasospasm and Grade 5 are by definition critically ill and unstable patients)
5. Critically ill patients who are unstable and who cannot undergo scans within the proposed timeline i.e. within 24 hours of the onset of their symptoms.

Patient identification/Recruitment/Consent:

Patients targeted for enrollment will be those referred to the Department of Neurosurgery and Neuroendovascular Surgery at University of Wisconsin meeting the inclusion criteria. Eligible candidates will be identified by the neuroendovascular or neurosurgical attending physician and will be invited to participate by a clinical care team member. If patients lack capacity to provide informed consent on their own behalf, the care team will include the next of kin in the consenting process. Subarachnoid hemorrhage patients that present with a medically unstable condition will not be considered for this study.

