All researchers and research staff involved in this project have completed Human Subjects and HIPAA training and are familiar with all procedures. The PI and co-investigators will review the data collected after the initial patients have been treated and outcome data becomes available. Adverse events or problems will be reviewed by the PI and co-investigators as they occur and will be reported to the IRB by the PI in accordance with posted guidelines. The PI and the co-investigators will meet regularly to review the data, adherence to the protocol and IRB guidelines. Data and safety monitoring will occur on a continuous basis by the research staff. The study team will meet regularly to review study progress including recruitment, data collection, and they will address any concerns or challenges that may arise. If initial pilot data shows that this technique is validated a formal study will be proposed to the IRB.

Statistical Considerations

The initial pilot study was conducted as a feasibility study and no robust statistical evaluation is possible. Since we have determined that the research imaging can be achieved safely and data reproducibly collected, we now hope to amend the cohort to a total of 30 patients so that we can capture more patients with vasospasm in order to have a more robust analysis of the correlation between percent change in CBF to Diamox and the future development of cerebral vasospasm.

IRB Concerns

The gold standard for determining if a patient has vasospasm is the clinical neurological exam. There is no currently accepted radiographic method or procedure for predicting vasospasm. Therefore, when comparing this proposed CBCT approach to the competing method we would be comparing it to the clinical neurological exam. Additionally, comparisons are being made to current methods of predicting vasospasm including TCDs, multidetector CTA/CTP, and angiography.

[figure not shown]
[figure not shown]

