With our initial 10 patients we are able to report that in all 10 patients the images were successfully required. We then performed an analysis of the 20 total cerebral hemispheres (right and left). Nineteen of 20 hemispheres demonstrated a significant change in CBF perfusion in response to Diamox ($p<0.05$). Six hemispheres demonstrated a 30% change in CBF and 12 had a 15% change. In 9 hemispheres there was the expected increase in CBF in response to Diamox. In 10 hemispheres there was a decrease in CBF. There was no statistical difference in the percent change between left and right hemispheres which would correlate with the global vasodilatory effects of Diamox. Symptomatic vasospasm then only developed in 2 of our patients. In one of these patients there was a pathological decrease in CBF in response to Diamox while the other had an appropriate increase in CBF. The goal of the analysis in this extension of the study is to better understand the changes in CBF in patients that go on to develop symptomatic or clinical vasospasm based on a change in neurological exam. Unfortunately, in our first phase of the pilot study only 2 patients developed symptomatic vasospasm. The reason we are requesting an extension to 30 patients is so we can capture a

larger number of patients with symptomatic vasospasm. Then we can assess our statistical analysis to see if we can consistently see a significant lack of response (either <30% increase in CBF or a decrease in CBF) to Diamox. With only 2 patients in our initial cohort developing symptomatic vasospasm it is impossible to make a more robust statistical proposal and that is why we are submitting a request to study more cases.

As discussed before, in this study design there is no need for a control group. We are comparing our CBCT information to the conventional method which is the clinical neurological exam change which indicates clinical or symptomatic vasospasm. The data that will be statistically compared is the pre-diamox perfusion in comparison to the post-diamox perfusion. A statistically significant change increase in CBF represents an appropriate response to Diamox. Lack of change in CBF or decrease in CBF could be suggestive of potential for developing vasospasm. More data with patients who develop clinical vasospasm is needed in order to correlate these changes with this subset of patients.

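### The prediction aim is judged on patients with vasospasm alone, yet the pilot's own counts suggest non-response is common in everyone; it needs a patient-level comparison with those who stay free of vasospasm

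*Combined protocol and SAP*

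**What the plan says.** The Data and Safety Monitoring Plan makes the next step conditional: "If initial pilot data shows that this technique is validated a formal study will be proposed to the IRB". It does not say what validated means.

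The Inclusion criteria section sets the size: "A total of 30 subjects will be enrolled in this pilot feasibility study". IRB Concerns reports on the first 10: "Symptomatic vasospasm then only developed in 2 of our patients". The extension is meant to capture more such patients and then "see if we can consistently see a significant lack of response (either <30% increase in CBF or a decrease in CBF) to Diamox". No proportion, interval or accuracy measure is attached to *consistently*.

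The same section gives a second, looser description of an abnormal result: "Lack of change in CBF or decrease in CBF could be suggestive of potential for developing vasospasm". It also states that the design needs no control group, and that the data to be compared statistically are perfusion before and after the drug.

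Statistical Considerations and the end of IRB Concerns name the aim of the expanded study as correlating percent CBF change with later vasospasm. The readable text gives no method for that correlation. Its only significance level, 0.05, belongs to a paired t-test over 40 slices within one hemisphere.

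**The concern.** A finding predicts an outcome only if it is more frequent in patients who go on to the outcome than in those who do not. A criterion that looks at cases alone measures sensitivity, and sensitivity is high for any finding that nearly everyone has. The pilot suggests that this is the situation here: by the definition with the 30% cut-off, most hemispheres are non-responders, yet few patients developed symptomatic vasospasm.

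The one test that is described does not fill the gap. A pre/post t-test shows whether CBF changed in a hemisphere. It cannot show whether the change separates patients by later outcome.

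At stake is whether the 30 patients can tell the team if the test merits a formal study. On the stated criterion, an uninformative test can look predictive.

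**Working it through.** **Inputs**
- Total enrolment 30 (Inclusion criteria); 2 of the first 10 patients with symptomatic vasospasm (IRB Concerns). Expected cases: 30 × 2/10 = 6, leaving 24 non-cases. The exact 95% interval for 2/10 is 2.5% to 55.6%, so 6 is only a working figure.
- Hemispheres (IRB Concerns): 20 in all, 19 with a significant change, 9 with an increase, 10 with a decrease, 6 with a 30% change (direction not given).

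The documents give no power, error rate or decision threshold, so there is no such figure to reproduce. The counts do agree with each other: 9 + 10 = 19.

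**Non-response rate, q**
- Definition A (less than 30% increase, or a decrease): reading 30% change as at least 30%, at most 6 of 20 hemispheres are responders. So q ≥ 14/20 = 70%. If some of the six were decreases, q is higher.
- Definition B (no increase): q = (20 − 9)/20 = 55%.

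Both rates include the two cases. No rule for combining hemispheres is stated, so hemisphere rates stand in for patient rates. For scale, at q = 70% with independent hemispheres, calling a patient a non-responder if either hemisphere is gives 1 − 0.3² = 91%; requiring both gives 0.7² = 49%.

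**Chance that an uninformative test shows non-response in most cases**

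Uninformative means the same q in cases and non-cases. With X ~ Binomial(6, q), P(X ≥ r) = Σ C(6,k) q^k (1 − q)^(6−k), summed over k from r to 6. At q = 0.70, P(X ≥ 4) = 0.324 + 0.303 + 0.118 = 0.744.

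| q | ≥4 of 6 | ≥5 of 6 | 6 of 6 |
|---|---|---|---|
| 55% (B) | 44% | 16% | 3% |
| 70% (A, minimum) | 74% | 42% | 12% |
| 85% (A, assumed) | 95% | 78% | 38% |

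**What non-cases add**

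Suppose all 6 cases and 17 of 24 non-cases (71%) were non-responders. One-sided Fisher p = C(23,6)/C(30,6) = 100,947/593,775 = 0.17. Perfect consistency among cases would then still be weak evidence.

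**A comparison that uses both groups**

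Take an observed AUC of at least 0.70 as an example threshold. Under no discrimination, the exact Mann–Whitney distribution (no ties) gives the false-go rate:

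| Cases vs non-cases | U needed | False-go rate |
|---|---|---|
| 6 vs 24 | ≥101 of 144 | 7.1% |
| 4 vs 26 | ≥73 of 104 | 11.0% |
| 3 vs 27 | ≥57 of 81 | 14.2% |

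With 6 vs 24 and a true AUC of 0.80, a binormal simulation passes this threshold 84% of the time. The interval is wide: at an observed AUC of 0.70 the Hanley–McNeil standard error is 0.130, so the 95% interval is 0.70 ± 1.96 × 0.130, or 0.44 to 0.96.

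**The case against.** Five points on the other side have force.

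1. The go sentence and the word *consistently* stand in different sections and nothing links them. Validated could refer to imaging performance, since Study Objective follows a paragraph that uses the word for the imaging technique. This stands: the link is an inference. But the expanded study's stated main aim is the relation to vasospasm, and the readable text offers no other criterion for it.

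2. The correlation aim implies some use of patients without vasospasm, and their scans and outcomes will be collected. This also stands. The gap is that no method uses them, not that the data are absent.

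3. A reader might infer that a useless test would usually pass. The documents do not support that. With 6 cases the chance runs from 3% (definition B, all six) to 74% (definition A at its minimum, four of six), and higher if q exceeds 70%. The result depends on which definition and which reading of *consistently* is used, and the plan fixes neither.

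4. A reader might also infer that the rule has already shown it cannot fail, because Study Objective says "Having so far achieved our objectives with the initial 10 patients we now hope to amend the protocol to allow for the larger cohort" although the two cases were split: "In one of these patients there was a pathological decrease in CBF in response to Diamox while the other had an appropriate increase in CBF". That misreads the statement. The sentences just before it concern reproducibility, ease of acquisition and safety, and nowhere is prediction claimed to have succeeded. The size of the second patient's increase is not given either, so under definition A that patient may still be a non-responder. The statement can stay.

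5. This is a pilot, its scans do not guide care, and a false pass leads only to a proposal. That limits the consequence. It does not make a case-only criterion informative.

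The figures and slides are not shown, so a criterion there cannot be ruled out.

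**Conclusion.** The concern holds in a limited form. The readable criterion for prediction looks only at patients with symptomatic vasospasm, and the only described test is pre versus post. Because at least 70% of pilot hemispheres were non-responders under the 30% definition, non-response in most cases would not by itself show prediction. An uninformative test could often give that picture: 74% for at least 4 of 6 cases and 42% for at least 5 of 6, falling to 44% and 16% under the no-increase definition.

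These figures assume 6 cases, hemisphere rates used as patient rates, and 30% change meaning at least 30%. They illustrate the weakness of the criterion; they are not the plan's error rate, which cannot be computed while the criterion is open. The point is worth correcting before the remaining outcomes are read, but it does not bear on the safety or feasibility aims.

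**What to change.** In Statistical Considerations and IRB Concerns, replace the case-only criterion with a patient-level comparison of percent CBF change between patients with and without symptomatic vasospasm. Use one value per patient, by a stated rule for combining hemispheres, and report the AUC with its 95% confidence interval. In the Data and Safety Monitoring Plan, base any statement that the technique is validated for prediction on that comparison.

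If a go threshold is wanted, fix it before the remaining outcomes are read and give its false-go rate by number of cases. The 0.70 above is an example, not a value from the documents; its rates are about 7% with 6 cases, 11% with 4 and 14% with 3. State also below how many cases the result will be called inconclusive.

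The cost is a short protocol revision, a hemisphere rule and one simple analysis, with no extra patients or scans. The downside is that the study may end as negative, or as inconclusive with a wide interval.

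### Two response rules are stated after the first 10 patients' CBF results were read against vasospasm; fix one rule now and report the first 10, the new 20 and the pooled 30 side by side

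*Combined protocol and SAP*

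**What the plan says.** Study Objective: "Thus far in the pilot study we have enrolled a total of 10 patients and are now planning to expand enrollment to 30 patients". The inclusion criteria repeat the total: "A total of 30 subjects will be enrolled in this pilot feasibility study". Statistical Considerations gives the reason for expanding: "we now hope to amend the cohort to a total of 30 patients so that we can capture more patients with vasospasm". The intended analysis there is a correlation between percent change in CBF and later vasospasm, and the end of IRB Concerns calls this association the main aim of the expanded study.

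IRB Concerns also reports the pilot. Of 20 hemispheres, 19 changed significantly (9 up, 10 down); 6 are described as showing a 30% change and 12 a 15% change. On outcome: "Symptomatic vasospasm then only developed in 2 of our patients". And: "In one of these patients there was a pathological decrease in CBF in response to Diamox while the other had an appropriate increase in CBF".

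Two descriptions of an abnormal response follow those results.
- **Rule A** looks for "a significant lack of response (either <30% increase in CBF or a decrease in CBF) to Diamox".
- **Rule B**, in the next paragraph, treats a statistically significant rise as appropriate, and no change or a fall as suggestive of vasospasm risk. It has no 30% threshold.

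The Data and Safety Monitoring Plan adds: "The PI and co-investigators will review the data collected after the initial patients have been treated and outcome data becomes available". It also provides for regular meetings to review data, and says a formal study will be proposed if the pilot data show that the technique is validated.

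The visible text does not choose between the rules, say when the 30% cut was set, or say whether the first 10 are analysed with the new 20 or apart from them.

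**The concern.** A response rule should be fixed before it is compared with outcomes. Here a third of the planned patients have been compared already, and the text still carries two rules. If the choice is left to the analysis, it can be made, even without intent, in the light of how each rule treats cases already known. Any resulting optimism enters the pooled 30 through the first 10. It would affect the association that the expansion is meant to estimate, and possibly the judgement that the technique is validated.

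**Working it through.** **1. How much has been seen.** The plan gives no sample-size calculation to reproduce; the only arithmetic is 30 - 10 = 20 new patients. Already seen: 10/30 = 33% of patients. Pilot cases: 2/10 = 20%, exact 95% CI 2.5% to 55.6%. With case rate p in the new 20, expected new cases are 20p and the share of all cases already seen is 2/(2 + 20p):

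| Assumed p | New cases | All cases | Share already seen |
|---|---|---|---|
| 10% | 2 | 4 | 50% |
| 20% | 4 | 6 | 33% |
| 30% | 6 | 8 | 25% |
| 40% | 8 | 10 | 20% |

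**2. The two rules on the pilot.**
- Hemispheres, Rule B: 10 falls plus 20 - 19 = 1 without significant change gives 11 of 20 flagged.
- Hemispheres, Rule A: if a 30% change means at least 30% in either direction, at most 6 can be rises of 30% or more, so at least 20 - 6 = 14 of 20 are flagged.
- Case with a fall: flagged by both rules.
- Case with a rise: not flagged by Rule B. Flagged by Rule A if the rise was below 30%, and not flagged otherwise. The size of the rise is not given.

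Pilot sensitivity is therefore 1/2 under Rule B, and either 1/2 or 2/2 under Rule A. The choice can change the class of 1 of the 2 known cases.

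**3. Size, if the rule were picked on the pilot.** These assumptions are not from the documents: CBF change is normal with SD 25% and mean 0% or 5%, there is no association with vasospasm, and there are 2 cases in the first 10 and 4 in the next 20. A patient is flagged when the change is below the cut. A cut of 30% is Rule A; a cut of 0% approximates Rule B. Whichever cut gives the larger sensitivity + specificity - 1 in the first 10 is kept. Simulated means:

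| | First 10 | Pooled 30 | New 20 |
|---|---|---|---|
| Better of 0% and 30% picked on the first 10 | 0.16 | 0.05 | 0.00 |
| One cut fixed beforehand (0% or 30%) | 0.00 | 0.00 | 0.00 |

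Results are the same at either mean. The pooled figure can be checked by hand: the first 10 supply 2/6 of the cases and 8/24 of the non-cases, both one third, so the pooled value is (1/3)(0.16) + (2/3)(0.00) = 0.05.

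**4. Precision in the new 20.** At p = 20%, 20 x 0.20 = 4 cases are expected, and the chance of 0 or 1 is 0.07. If all 4 of 4 were flagged, the exact 95% CI for sensitivity would be 0.025^(1/4) = 40% to 100%.

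**The case against.** A reader might infer that the 30% cut was derived from the pilot, or that the pooled result must be optimistic. The documents support neither. The cut appears after the pilot results, but nothing says that it came from them, and the second row of the table in step 3 shows no bias if one rule was set beforehand. The direction of the hypothesis, no expected rise in impaired patients, already stands in the introduction and background.

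Nor do the pilot data visibly flatter a rule. If each case's two hemispheres moved together, a fall flags 2 of 4 case hemispheres and 8 of 16 others, so sensitivity + specificity - 1 is 0.50 - 0.50 = 0. Rule B gives 0.50 - 9/16 = -0.06. Rule A cannot be placed more closely than 0.50 - 16/16 = -0.50 to 1 - 10/16 = 0.38. The 0.16 in the working is therefore not an estimate for this pilot.

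Three further points have force. The planned analysis is a correlation with percent change; used as a continuous measure, it needs no cut, and no sensitivity or specificity is planned. Review of CBF by outcome while patients accrue is not excluded, but it is not planned either: the quoted sentence concerns the initial patients, and Scan procedure defers formal evaluation of the scans to a later date. The slides that IRB Concerns cites for the percent-change calculation are not visible and may define the per-patient summary. Finally, this is a feasibility study, and a formal study would follow.

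These points limit the size of the concern but do not remove it. The text still states two rules after outcomes were known, wants to see whether cases consistently show the lack of response that Rule A defines, and does not say how the first 10 enter the analysis.

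**Conclusion.** The point holds as an inexpensive improvement to the plan. It does not show that the result is biased. The 30 include 10 patients already read against outcome, and the two rules written beside those results can class one of the two known cases differently. That the 10 will be pooled is itself inferred from the stated total of 30; nothing excludes them.

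Any optimism is conditional. It is zero if one rule was fixed beforehand, and about 0.05 in the pooled 30 if the choice between 0% and 30% is made on the pilot, under the assumptions in step 3. Seen cases make up about a third of the expected total at a 20% rate, and 20% to 50% for rates from 40% down to 10%. With no formal predictive test planned, what is at risk is an over-favourable description of the association, not a planned type I error rate.

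A reader might also conclude that only the new 20 should count. That is a trade-off and not a requirement: with about 4 expected cases, the new 20 alone say little.

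**What to change.** In the Data and Safety Monitoring Plan, Statistical Considerations and IRB Concerns:

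1. State one response rule and one per-patient CBF summary now, before any new patient's CBF result is seen beside an outcome. Say whether the 30% cut was set before the pilot results. If the slides already define the summary, cite them in the text.
2. Report the association between CBF response and vasospasm for the first 10, the new 20 and the pooled 30 side by side, with the first 10 labelled exploratory. Call the technique validated only if the new 20 are consistent with the pooled result.
3. State that the regular reviews cover safety, recruitment and image quality, and that no table of CBF response by outcome is made until outcomes are complete.

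The cost is protocol wording; no patient or scan is added. The drawback is that the estimate in the new 20 is imprecise (step 4), which is why the pooled estimate stays beside it.
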